1.0 General Information

***Enter the full title of your study:**

Validation of PET/MRI integrated system acquisition for cardiac applications

***Enter the study number or study alias**

Validation of cardiac PET MR

* This field allows you to enter an abbreviated version of the Study Title to quickly identify this study.

5.0 Initial Screening Questions - Updated 9/13

(Note: You must answer every question on this page to proceed).

If you are converting to the new form, check questions 5.4, 5.6, 5.7, 5.8 and 5.10 before saving and continuing to the next section.

5.1 * Application type:

- Full Committee
- Expedited
- Exempt

5.2 * Risk level (Help Text updated 9/13):

- Minimal risk
- Greater than minimal risk

5.3 * Subject contact:

- Yes (including phone, email or web contact)
- No (limited to medical records review, biological specimen analysis, and/or data analysis)

5.4 * Funding (past or present):

- Funded or will be funded (external sponsor, gift, program or specific internal or departmental funds)
- Unfunded (no specific funds earmarked for this project)

Unfunded student project

5.5 * The Principal Investigator and/or one or more of the key study personnel has financial interests related to this study:

Yes No

If Yes, the Conflict of Interest Advisory Committee (COIAC) office may contact you for additional information.

5.6 * This is an investigator-initiated study:

Yes No

5.7 * This study ONLY involves retrospective records review and/or identifiable biospecimen analysis:

Yes No

5.8 * This is a clinical trial:

Yes No

Clinical Trial Registration

"NCT" number for this trial:

NCT02062008

5.9 * This is a multicenter study:

Yes No

5.10 * This application involves the study of unapproved or approved drugs, devices, biologics or in vitro diagnostics:

Yes No

5.11 * This application involves a Humanitarian Use Device:

No

Yes, and it includes a research component

Yes, and it involves clinical care ONLY

5.12 * This study involves human stem cells (including iPS cells and adult stem cells), gametes or embryos:

No

Yes, and requires CHR and GESCR review

Yes, and requires GESCR review, but NOT CHR review

5.13 * This is a CIRB study (e.g. the NCI CIRB will be the IRB of record):

Yes No

5.14 * This application includes a request to rely on another IRB (other than NCI CIRB):

Yes No

Note: If this request is approved, the CHR will **NOT** review and approve this study. Another institution will be the IRB of record.

6.0 Funding

6.1 Identify all sponsors and provide the funding details. If funding comes from a Subcontract, please list only the Prime Sponsor: **Note: we require only a P Number OR an A Number for funding coming through UCSF. Please avoid these common errors in funding documentation:**

- **DO NOT add the A Number if a P Number was already provided OR update the A Number field when a new funding cycle begins. The IRB does NOT use this information or want these changes made.**
- **DO NOT add a grant continuation as a new funding source.**

External Sponsor:

View Details	Sponsor Name	Sponsor Type	Awardee Institution	Contract Type:	UCSF RAS "P number" or eProposal number	UCSF RAS System Award Number ("A" + 6 digits)
 GE Medical Systems	GE Medical Systems	04	UCSF	Grant	P0501481	

Sponsor Name:	GE Medical Systems
Sponsor Type:	04
Sponsor Role:	Funding
CFDA Number:	
Grant/Contract Number:	CA-0050676
Awardee Institution:	UCSF
Is Institution the Primary Grant Holder:	Yes
Contract Type:	Grant
UCSF RAS "P number" or eProposal number:	P0501481
UCSF RAS System Award Number ("A" + 6 digits):	
Grant Number for Studies Not Funded thru UCSF:	
Grant Title:	
PI Name: (If PI is not the same as identified on the study.)	
Significant Discrepancy:	

Gift, Program, or Internal Funding (check all that apply):

- Funded by gift (specify source below)
- Funded by UCSF or UC-wide program (specify source below)
- Specific departmental funding (specify source below, if applicable)

List the gift, program, or departmental funding source:

6.2 If you tried to add a sponsor in the question above and it was not in the list, follow these steps:

- If funding has already been awarded or the contract is being processed by the Office of Sponsored Research (OSR) or Industry Contracts Division (ICD), your sponsor is already in the system and the project has an eProposal Proposal or Award number. Check with your department's OSR Staff or ICD Officer to ask how the sponsor is listed in the UC sponsor list and what the Proposal or Award number is. [Click here to find your OSR staff](#) and [here to find your ICD staff](#).
- If your sponsor is not yet in the list, enter it in the box below.

Sponsor not in list

Only if your sponsor is not yet in the list, type the sponsor's name:

If the funding is administered by the UCSF Office of Sponsored Research, your study will not receive CHR approval until the sponsor and funding details have been added to your application.

6.3 * This study is currently supported in whole or in part by Federal funding OR has received ANY Federal funding in the past ([Help Text updated 9/13](#)):

Yes No

If yes, indicate which portion of your grant you will be attaching:

- The Research Plan, including the Human Subjects Section of your NIH grant or subcontract
- For other federal proposals (contracts or grants), the section of the proposal describing human subjects work
- The section of your progress report if it provides the most current information about your human subjects work
- The grant is not attached. The study is funded by an award that does not describe specific plans for human subjects, such as career development awards (K awards), cooperative agreements, program projects, and training grants (T32 awards) OR UCSF (or the affiliate institution) is not the prime recipient of the award

8.0 Study Design

8.1 * Study design (Help Text updated 9/13):

The goal of this study is to understand how simultaneous PET/MR acquisition can provide novel qualitative and quantitative information to guide clinical intervention and predict prognosis of patients with risk factors for the development of coronary artery disease, or with diagnosis of cardiovascular ischemic or inflammatory disorders.

Patients required to have a clinical cardiac FDG PET or PET/CT imaging study as part of standard of care, to detect myocardial viability or a cardiac inflammatory process will be enrolled in the study. After the initial acquisition of the clinical study patients will be immediately imaged in the PET/MRI system, with no additional administration of any radiopharmaceutical. The main purpose of the study would then be to compare the information provided from the clinical PET/CT with the one from the simultaneous cardiac PET/MRI.

8.2 If this is a clinical trial, check the applicable phase(s) (Help Text updated 9/13):

- Phase I
- Phase II
- Phase III
- Phase IV

9.0 Scientific Considerations

9.1 Hypothesis (Help Text updated 9/13):

This study has a hypothesis:

Yes No

If yes, state the hypothesis or hypotheses:

We hypothesize that simultaneous acquisition of cardiac PET/MRI can provide some other benefits in comparison to stand alone scanners.

- In a hybrid system, real-time MR-based motion detection and correction could be applied since cardiac and respiratory gating can be image-based without external sensors. This could allow partial-volume correction and event-based correction of patient motion during the PET acquisition.
- Combined metabolic information provided by FDG and structural information offered by MRI can help to better define the extent, location and significance of infarcted myocardium or viable tissue, with special significance for non-transmural or transmural lesions.
- The lack of exposure to ionizing radiation and iodinated contrast agents makes hybrid PET/MRI attractive when compared with PET/CT.
- Both cardiac MRI and PET examinations can be rather time consuming. Thus, improvements in patient compliance as a result of reduced scan time could be significant, particularly in patients with dyspnea due to heart failure who have difficulty holding their breath during MRI acquisitions.
- Increased patient throughput based on reduced scan times is also likely to be cost-effective.

9.2 * List the specific aims:

- To compare regional myocardial uptake of FDG on images obtained on a standard PET camera with the new PET/MR camera, in patients with and without overt diagnosis of ischemic coronary artery disease.
- To compare viability maps obtained with cardiac MR images and FDG-PET for delineation of myocardial infarct core and border zone, in patients with coronary artery disease.
- To correlate MRI myocardial strain with relative myocardial FDG uptake in patients with a previous myocardial infarction, referred for a clinical myocardial viability study.
- To interrogate if simultaneous acquisition of cardiac PET and viability cardiac MR differ from acquisitions obtained independently, with special focus on attenuation correction methods.
- To combine MRI scar map with FDG-PET uptake in patients with cardiac sarcoidosis and myocarditis.
- To evaluate cardiac strain and myocardial scar burden in obese patients with and without diabetes.

9.3 Statistical analysis:

Correlation coefficient and Bland Altman plots will be applied to evaluate the agreement between linear variables obtained from PET and cardiac MRI.

9.4 If this study has undergone scientific or scholarly review, please indicate which entity performed the review:

Cancer Center Protocol Review Committee (PRC) (Full approval is required prior to final CHR approval for cancer-related protocols.)

CTSI Clinical Research Center (CRC) advisory committee

Departmental scientific review

Other:

Specify Other:

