is limited by the low resolution of the PET compared to that of MRI. Here, MRI is clearly the modality-of-choice to quantitate cardiac function, such as volumes, mass, ejection fraction and regional wall thickening. Determination of LV function is essential for the diagnosis of heart failure and its prognostic value is well established. Therefore, its combination with any other imaging parameter is likely to provide incremental information.

Myocardial viability

Ischemic myocardium that is dysfunctional but viable has the potential for recovery of contractile function after revascularization. Evaluation of myocardial glucose utilization with 18F -FDG PET is considered as the most reliable tool to assess myocardial viability. Its quantitative nature allows assessment of the amount of viable tissue as a continuum from fully viable, through partially viable in the

areas of non-transmural infarction, to non-viable scar. Contrast-enhanced MRI appears to be a promising alternative capable of visualizing transmural distribution of viable and infarcted myocardium with excellent spatial resolution. Contrast-enhanced MRI of myocardial infarction is based on the delayed-enhancement technique using inversion-recovery prepared T1-weighted gradient-echo pulse

sequences after intravenous administration of Gd-DTPA. Infarcted myocardium appears enhanced relative to normal myocardium when imaged with a delay (typically 5–20 min) after intravenous injection of the contrast agent due to

different wash-out kinetics. A comparison of delayed-enhancement MRI with 18F FDG PET and 13NH_3 in 31 patients with ischemic heart failure revealed that the location and extent of infarct scarring as delineated by delayed enhancement correlated very well with the non-viable segments from PET. The main source of difference between the methods was related to the presence of non-transmural enhancement in regions that were viable on PET. This can be explained by the higher spatial resolution of MRI compared with nuclear imaging methods that makes delayed-enhancement suitable for the detection of small areas of subendocardial infarcts. An improved contractile performance after intervention is commonly considered as the gold standard for assessing myocardial viability,

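### Hypothesis 2 claims that combining FDG and MRI delineates infarct better, but PET-MRI agreement, the only planned statistic, can neither support nor refute it

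*Combined protocol and SAP*

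**What the plan says.** Section 9.1 opens with the general hypothesis that simultaneous PET/MRI "can provide some other benefits in comparison to stand alone scanners". Its second bullet says that metabolic information from FDG and structural information from MRI, taken together, "can help to better define the extent, location and significance of infarcted myocardium or viable tissue", and it singles out the transmural versus non-transmural distinction.

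The nearest aim in 9.2, which is limited to coronary artery disease, reads: "To compare viability maps obtained with cardiac MR images and FDG-PET for delineation of myocardial infarct core and border zone". Section 8.1 gives the main purpose as to "compare the information provided from the clinical PET/CT with the one from the simultaneous cardiac PET/MRI".

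Section 9.3 is one sentence: "Correlation coefficient and Bland Altman plots will be applied to evaluate the agreement between linear variables obtained from PET and cardiac MRI". It names no variables, agreement margin, target correlation or rule for interpreting disagreement.

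In 10.2, an earlier comparison of delayed-enhancement MRI with PET is summarised: "The main source of difference between the methods was related to the presence of non-transmural enhancement in regions that were viable on PET". The next sentence gives the reason: "This can be explained by the higher spatial resolution of MRI compared with nuclear imaging methods". The same section states that "An improved contractile performance after intervention is commonly considered as the gold standard for assessing myocardial viability". Section 17 describes a single imaging session and no follow-up of contractile function.

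**The concern.** The hypothesis is about complementarity: two modalities together delineate tissue better than one. The statistic measures how far the two modalities give the same answer. These are different questions. If PET and MRI agreed perfectly, MRI would add nothing to FDG on that variable. If they disagree, agreement statistics cannot say whether MRI saw something real or was wrong.

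The background makes this concrete. The difference it reports between the modalities is non-transmural scar that MRI resolves and PET does not, which is the lesion type that hypothesis 2 emphasises. If infarct extent is the variable compared under 9.3, such lesions enter as bias and scatter.

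What is at stake is whether the pilot yields anything usable on hypothesis 2. Section 11.4 says that its data should feed a sample size calculation for a larger trial. A correlation and a pair of limits would not supply the discordance rate needed to plan a study of added value.

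**Working it through.** **Step 1: is there a figure to reproduce?** No. The sample size (60 in 11.1 and 11.2, 50 in 11.4) is not derived from any effect size, SD, margin or power. All inputs below are assumptions, chosen to test direction and ambiguity rather than to predict results.

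**Step 2: can one agreement result mean different things?** Let scar seen by both modalities have mean 15 and SD 8 (variance 64), in percent of left ventricle. Let MRI also see extra true scar with SD σB, and let PET and MRI have error SDs σP and σM. Then:

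- r = 64 / √[(64 + σP²)(64 + σB² + σM²)]
- half-width of limits = 1.96 √(σB² + σP² + σM²)
- gain = R²(truth given PET and MRI) − R²(truth given PET)

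| Setting | σB, σP, σM | r | Half-width | R², PET alone | R², PET and MRI | Gain |
|---|---|---|---|---|---|---|
| MRI sees scar that PET misses | 4, 3, 3 | 0.79 | 11.4 | 0.70 | 0.92 | 0.22 |
| MRI measures the same scar more precisely | 0, 5, 3 | 0.79 | 11.4 | 0.72 | 0.91 | 0.19 |
| MRI is merely noisier | 0, 3, 5 | 0.79 | 11.4 | 0.88 | 0.91 | 0.03 |

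In every row r = 64/√(73 × 89) = 0.79 and the half-width is 1.96√34 = 11.4. Mean bias is 4 points in the first row and 0 in the others. Bias does not settle the matter: a constant MRI overestimate of 4 points in the third row would reproduce it without changing r, the limits' width or the gain.

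**Step 3: which way does agreement move as MRI adds information?**

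- MRI sees scar that PET misses (both error SDs 3; σB, and with it the mean extra scar, from 0 to 8): r falls from 0.88 to 0.64, bias rises from 0 to 8, limits widen from ±8.3 to ±17.8, and the gain rises from 0.06 to 0.50.
- Same scar, MRI error falling from 10 to 1 (PET error 5): r rises from 0.53 to 0.84 and the gain rises from 0.04 to 0.27.
- MRI only noisier, error rising from 3 to 9 (PET error 3): r falls from 0.88 to 0.62 and the gain falls from 0.06 to 0.01.

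The direction depends on the mechanism.

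**Step 4: the mechanism in 10.2, by segment.** Assume 60 patients with 17 segments each, a mean infarcted share of 27%, error SD of 4 points in each modality, MRI detecting all infarcted segments and FDG only the transmural ones.

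| Non-transmural share of infarcted segments | r | Bias (points) | Half-width (points) |
|---|---|---|---|
| 0% | 0.96 | 0 | 11 |
| 15% | 0.92 | 4 | 15 |
| 30% | 0.88 | 8 | 20 |
| 50% | 0.78 | 14 | 26 |

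A re-run with more replicates matched except for 0.79 in the last row. The bias is the non-transmural share times 27%: 0.15 × 27 = 4, 0.30 × 27 = 8, 0.50 × 27 = 14.

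**Step 5: what would a discordance analysis deliver?** Exact 95% intervals for an observed 50% of patients are 37–63% at 30/60, 36–64% at 25/50 and 31–69% at 15/30. The number with coronary artery disease is not given, so the widest is plausible. An outcome of at least one reclassified segment has a noise floor: with independent misclassification of 3% or 5% per segment (assumed), 1 − 0.97¹⁷ = 40% or 1 − 0.95¹⁷ = 58% of patients would qualify with no true added information.

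**The case against.** A reader might infer something stronger: that agreement always worsens as MRI contributes more, so a positive finding would be reported as failure. The documents do not support this. They set no margin, target correlation or success rule, and 11.4 calls the study a pilot, so no result is defined as failure. Nor is the direction general: in the second setting of Step 3, agreement and added information rise together.

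Other objections also carry weight.

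- The segment simulation builds in its decline, because FDG is set to miss every non-transmural lesion. Under that model the Bland-Altman bias recovers the mean extra MRI extent, with its sign, though not its location.
- Section 9.3 refers to linear variables without naming them. That infarct extent is one of them is an inference.
- Agreement is a reasonable description for the aim on viability maps and for FDG on the two cameras.
- The background shows that the investigators regard mismatch as informative: 10.1 raises it as a possible biomarker in sarcoidosis and myocarditis.
- The stem of the hypothesis compares with stand-alone scanners, so testing FDG plus MRI against FDG alone covers only one side.

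These points limit the claim and shape the remedy. They do not close the gap: nothing in 9.3 compares the combination with a single modality or with any reference.

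**Conclusion.** The point holds as a mismatch between hypothesis and analysis. Agreement between PET and MRI is non-diagnostic for hypothesis 2: in the worked example, r = 0.79 with limits of bias ± 11.4 points goes with R² gains from 0.03 to 0.22. Under the mechanism that the protocol itself describes, added MRI information would show as bias and wider limits and could be misread as poor performance. That direction is conditional on the mechanism, and misreading is a risk, not a planned conclusion.

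The sizes rest entirely on assumed scar distributions and error SDs. The conclusion that agreement cannot answer the question does not. It follows from the absence of a reference standard and of any combined-versus-single-modality comparison. This should be corrected, but it does not invalidate the study's descriptive aims.

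**What to change.** Keep correlation and Bland-Altman for FDG on the two cameras and as a description of the viability maps. For hypothesis 2, add to 9.3, restricted to patients with coronary artery disease:

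- A segment-level cross-classification of FDG viability by enhancement transmurality, using the cut-offs already quoted in 10.2 (50% of normal FDG uptake; 50% transmural scar). Keep absent enhancement as its own category, since the 50% scar cut-off alone would merge it with non-transmural enhancement.
- Per patient, the number and share of segments that are FDG-viable with non-transmural enhancement, and the discordance in the opposite direction, so that the combination is set against each stand-alone modality.
- 95% CIs that allow for clustering of segments within patients, for example by a patient-level bootstrap.
- Any proportion of patients with at least one reclassified segment as a secondary result only, with a sensitivity analysis for segment misclassification or misregistration.
- A statement that, without a recovery outcome, the result shows that combining modalities changes the delineation, not that the change is correct, and that hypothesis 2 is exploratory.

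The cost is a few sentences and segment scoring of images already planned in 17.1, with no extra scan, visit or patient. The downsides are wide intervals and a narrower claim than better delineation.

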although benefits of revascularization do not appear to be limited to improved function. In an initial study by Kim et al. in 41 patients with chronic ischaemic heart disease, dysfunctional segments with less than 25% of delayed enhancement were likely to recover after complete revascularization. In contrast, segments with more than 50% of delayed enhancement had a low probability ($<10\%$) of functional improvement. Comparable positive predictive values (73%) for functional recovery 6 months after revascularization were found for the lack of delayed enhancement (cut-off value less than 50% transmural scar) and the presence of preserved 18F -FDG uptake (cut-off value more than 50% of normal myocardium) as assessed by PET as the reference method to detect viable vs. nonviable myocardium. A recent meta-analysis of diagnostic studies indicated

that 18F -FDG PET has a higher sensitivity than delayed enhancement MRI (92% vs. 84%) in predicting functional recovery upon revascularization, while specificities were comparable (63%). The relatively low specificity of the techniques indicates that a substantial percentage of segments that are classified as viable by the imaging

techniques do not improve after revascularization. Although there are limited data on their combined use, adjunctive PET and MRI markers of viability, such as reduced diastolic wall thickness, lack of contractile response to inotropic stimulation with a low dose of dobutamine, preserved epicardial rim of viable myocardium, and preserved perfusion have been proposed to help refine the classification of dysfunctional segments as clinically viable or non-viable.

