11.0 Sample Size and Eligibility

11.1 Number of subjects that will be enrolled at UCSF and affiliated institutions:

60

11.2 Total number of subjects that will be enrolled at all sites (Help Text updated 9/13):

60

11.3 Estimated number of people that you will need to consent and screen here (but not necessarily enroll) to get the needed subjects:

120

11.4 Explain how and why the number of subjects was chosen (Help Text updated 9/13):

This is a pilot study and we anticipate a number of 50 patients to obtain data to generate a formal sample size calculation for a larger trial.

11.5 * Eligible age range(s):

- 0-6 years
- 7-12 years
- 13-17 years
- 18+ years

11.6 Inclusion criteria:

Subjects with ischemic and non-ischemic cardiac disease referred for cardiac PET for viability imaging.

11.7 Exclusion criteria:

Contraindications for MRI, including cardiac pacemaker, claustrophobia, retained metallic foreign body, cochlear implant, Aneurysm clip in the brain, pregnancy and eGFR less than 45%.

11.8 There are inclusion or exclusion criteria based on gender, race or ethnicity:

Yes No

If **yes**, please explain the nature and rationale for the restrictions:

12.0 Drugs and Devices**12.1 * Investigational drugs or biologics will be used OR approved drugs or biologics will be studied under this application:**

Yes No

12.2 * Investigational medical devices or in vitro diagnostics will be used OR approved medical devices or in vitro diagnostics will be studied under this application:

Yes No

12.3 * A Non-Significant Risk (NSR) determination is being requested for an investigational device:

Yes No

12.4 Verification of IND/IDE numbers: If the sponsor's protocol does not list the IND/IDE number, you must submit documentation from the sponsor or FDA identifying the IND/IDE number for this study. Attach this documentation in the Other Study Documents section of the Initial Review Submission Packet.

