17.0 Procedures

17.1 * Procedures/Methods [Help Text updated 9/13] For clinical research list all study procedures, test and treatments required for this study, including when and how often they will be performed. If there are no clinical procedures, describe the Methods:

The subjects will undergo PET/MR for study purposes after they have finished their clinically indicated PET/CT, with no additional venipuncture to the patients.

We propose to use 5D MR imaging (3D in space, in time through the cardiac cycle, and in time through the respiratory cycle) to provide improved information on the location of the signal source during PET acquisition.

Dynamic and static PET data will be acquired in list mode and retrospectively rebinned according to predicted location from MR data.

Accelerated MR methods (including compressed sensing) will be used to give rapid assessment of volumes over time.

Additional MR imaging sequences will include strain mapping and VEC-MRI for flow imaging. In addition gadolinium delayed enhancement will be obtained for myocardial tissue characterization with MRI.

If you have a procedure table, attach it to the submission with your other study documents.

17.2 Interviews, questionnaires, and/or surveys will be administered or focus groups will be conducted:

Yes No

List any standard instruments used for this study:

Attach any non-standard instruments at the end of the application.

17.3 Conduct of study procedures or tests off-site by non-UCSF personnel:

Yes No

If yes, explain:

17.4 Sharing of experimental research test results with subjects or their care providers:

Yes No

If yes, explain:

17.5 * Specimen collection for future research and/or specimen repository/bank administration:

Yes No

17.6 Time commitment (per visit and in total):

1 hour in the scanner.

17.7 Locations:

The cardiac MRI will take place at the China Basin radiology.

17.8 Describe the resources in place to conduct this study in a way that assures protection of the rights and welfare of participants:

1. The research team will make several efforts to keep the PHI under extreme security, including the use of a coded database, password protected computers and locked cabinets, which will all be kept inside a locked office at the Parnassus campus.
2. Patients are screened for prior claustrophobic symptoms using a screening form. Earplugs are provided to all patients in order to minimize the discomfort related to the loud noise.

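### Aim 3: a plain correlation of strain with relative FDG uptake, pooled over regions, mixes within- and between-patient relations and may understate the regional one

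*Combined protocol and SAP*

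**What the plan says.** The third aim in section 9.2 is "To correlate MRI myocardial strain with relative myocardial FDG uptake" in post-infarction patients referred for a clinical viability study. The word 'relative' is attached to FDG only.

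Section 9.3 gives one sentence for all six aims: "Correlation coefficient and Bland Altman plots will be applied to evaluate the agreement between linear variables obtained from PET and cardiac MRI".

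Three other places bear on how Aim 3 would be carried out:

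- Section 17.1: "Additional MR imaging sequences will include strain mapping and VEC-MRI for flow imaging". Regional strain values will therefore exist.
- Section 10.2, on viability, cites an FDG threshold expressed as a "cut-off value more than 50% of normal myocardium". This is the nearest the documents come to saying what relative uptake means.
- Section 10.1 motivates the work by a possible link between ischemia in the infarct border zone and strain, which is a question about regions of one heart.

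Section 11.4 gives the purpose of the pilot: "we anticipate a number of 50 patients to obtain data to generate a formal sample size calculation for a larger trial". The documents do not define 'relative' for Aim 3, and do not say whether strain is regional or global, or raw or scaled. They do not give the unit of analysis or say whether the correlation is within patients.

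**The concern.** Bland-Altman analysis needs two measurements of the same quantity on a common scale. Strain and relative FDG uptake are not that, so for Aim 3 section 9.3 reduces to a correlation coefficient.

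Uptake expressed against the patient's own myocardium has the patient's overall uptake level divided out. Strain, as worded, has had nothing of the kind done to it. If regions from all patients go into one coefficient, three things follow:

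- The result mixes two relations: whether poorly metabolising regions contract less than other regions of the same heart, and whether hearts with lower average relative uptake contract less overall.
- Patient-to-patient spread in strain that has nothing to do with relative FDG enters as noise and pulls the coefficient down.
- The usual interval counts regions of the same heart as independent observations.

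The estimate would then depend on how varied the recruited hearts are as well as on regional physiology. That makes it a weak basis for interpretation, and for later planning if Aim 3 is used for that.

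**Working it through.** **Plan's own figure.** There is none to reproduce. The documents give no correlation, power or precision figure for Aim 3, and no ICC or SD for either measure. Every input below is an assumption, chosen to show a range. Strain is taken as a magnitude, so larger means better contraction.

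**Formula.** With regions pooled over patients,

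r_pooled = r_between × √(ICC_strain × ICC_FDG) + r_within × √[(1 − ICC_strain)(1 − ICC_FDG)],

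where each ICC is the share of that measure's variance lying between patients.

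**Case A: relative FDG has no patient-level variance (ICC_FDG = 0).** The first term vanishes and r_pooled = r_within × √(1 − ICC_strain). For r_within = 0.60:

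| ICC_strain | Calculation | r_pooled |
|---|---|---|
| 0.1 | 0.60 × √0.9 | 0.57 |
| 0.2 | 0.60 × √0.8 | 0.54 |
| 0.3 | 0.60 × √0.7 | 0.50 |
| 0.5 | 0.60 × √0.5 | 0.42 |

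**Case B: patient means of relative FDG do vary, for example with infarct extent.** Take r_within = 0.60, ICC_strain = 0.3 and ICC_FDG = 0.2. The weights are √(0.3 × 0.2) = 0.245 on the between-patient term and √(0.7 × 0.8) = 0.748 on the within-patient term.

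- r_between = 0: 0.60 × 0.748 = 0.45.
- r_between = 0.6: 0.147 + 0.449 = 0.60.
- r_between = 0.8: 0.196 + 0.449 = 0.65.

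The pooled value can therefore lie below, at or above the within-patient value. Break-even is r_between = r_within × [1 − √((1 − ICC_strain)(1 − ICC_FDG))] / √(ICC_strain × ICC_FDG). With ICC_strain = 0.3 this is 0.62 at ICC_FDG = 0.2 and 0.90 at ICC_FDG = 0.05. The less patient-level variance relative FDG retains, the harder it is to avoid understatement.

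**Simulation.** The set-up was 50 patients × 17 segments with 200 replicates per row. FDG was divided by the patient's maximum. Strain was 15 × viability, plus a patient offset, plus noise of SD 3. Infarct extent averaged 30% of segments and was either fixed or varied with SD 20 percentage points.

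| Infarct extent | Offset SD | ICC_strain | Pooled r | Within-patient r | r of patient means |
|---|---|---|---|---|---|
| Fixed | 0 | about 0 | 0.75 | 0.76 | 0.23 |
| Fixed | 3 | 0.29 | 0.62 | 0.76 | 0.07 |
| Fixed | 4 | 0.42 | 0.56 | 0.76 | 0.02 |
| Varying | 0 | 0.05 | 0.75 | 0.74 | 0.81 |
| Varying | 3 | 0.33 | 0.63 | 0.74 | 0.35 |
| Varying | 4 | 0.46 | 0.57 | 0.74 | 0.29 |

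The within-patient estimate hardly moves. The pooled estimate falls only when strain carries a patient offset of its own. The correlation of patient means moves most of all, because it addresses a different relation: average uptake, which reflects infarct extent, against overall strain.

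**Interval.** In this layout the ordinary formula would count 50 × 17 = 850 independent pairs, although they come from 50 hearts. How far that misstates the uncertainty cannot be worked out from the documents.

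**The case against.** The strongest reply is that the plan has not committed itself to a mismatched analysis; it has only been brief. Aim 3 does not say regional, whereas Aim 1 does ("To compare regional myocardial uptake of FDG on images obtained on a standard PET camera with the new PET/MR camera"). 'Relative' is undefined, and the scaling of strain is simply not mentioned. With one value per patient the attenuation formula does not apply. This stands as a limit: pooling over regions is an inference from the border-zone rationale, the strain mapping and the percent-of-normal threshold, not something the plan states. It does not remove the point, because a patient-level coefficient would not answer the regional question that motivates the aim.

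A reader might go further and infer that patient differences in strain have no counterpart in relative FDG, so that the coefficient must be biased toward zero. The documents do not support that. Scaling removes a patient's overall uptake level but leaves differences in infarct extent, and a larger infarct can lower both mean relative uptake and overall strain. Case B and the varying-extent row with no offset show that the loss can vanish or reverse. The mention of heart failure in section 9.1 concerns breath-holding and scan time; it says nothing about the spread of strain in Aim 3 patients.

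A reader might also convert the attenuated values into required sample sizes for the larger trial. That does not follow. The usual correlation formula counts independent pairs, which regional values are not, and section 11.4 does not say which aim or parameter will size that trial.

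Finally, this is one of six aims in a self-described pilot, with no hypothesis test or target correlation for it. That is a fair limit on its weight.

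**Conclusion.** The point holds in conditional form. A plain correlation coefficient is the wrong tool for pooled regional values: it blends two relations, and its usual interval ignores clustering. It may understate the regional relation, and does so when strain has patient-level variation unrelated to relative FDG.

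Under the assumption that relative FDG has no patient-level variance, a within-patient 0.60 would read 0.54 to 0.42 for strain ICCs of 0.2 to 0.5. With varying infarct extent and no separate strain offset, the loss is nil or negligible. Direction and size both rest on variance components that the documents do not give, and the whole point rests on the regional reading of Aim 3. A change is worth making because a better method is available at the cost of wording; the documents do not show that the Aim 3 result is bound to be wrong.

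**What to change.** In section 9.3, add a separate statement for Aim 3:

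1. The analysis uses regional values of strain and of relative FDG uptake. Relative uptake is regional uptake as a percentage of the patient's own reference myocardium, with the reference region named.
2. The association is estimated by repeated-measures correlation, or by a mixed model of regional strain on relative FDG with a patient intercept. If the intercept is random, enter FDG as the deviation from the patient's mean alongside that mean, so that the slope is purely within-patient.
3. The interval comes from that model, or from resampling whole patients.
4. The patient-level association (mean strain against mean relative FDG) is reported separately and labelled as such.
5. The within- and between-patient variances of both measures are reported, since the documents have none and later planning would need them.

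Dividing strain by its value in the FDG reference region is not a substitute for item 2. The ratio has a noisy denominator and does not act as a patient intercept. In an illustrative simulation with assumed inputs (50 patients × 16 segments, strain offsets of SD 3, 4 and 6), pooled r with strain so scaled was 0.63, 0.61 and 0.57, against a within-patient r of 0.67 to 0.68.

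The cost is analysis wording only, because strain mapping and FDG imaging are already planned. The small downside is that the within-patient estimate does not describe differences between patients in global function, which is why item 4 is reported beside it.
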